## 1 Background

Since the 21st century, the number of diabetes mellitus (DM) cases worldwide has increased rapidly. According to the International Diabetes Federation, in 2021, 537 million adults had diabetes globally, and it is expected that by 2045, this number will exceed 780 million. China has the highest number of diabetes-related deaths each year, approximately 10,000. Nearly half of type 2 diabetes mellitus type 2 (T2DM) will develop into diabetic kidney disease (DKD) . DKD has the characteristics of high prevalence, many pathogenesis mechanisms, and lack of effective strategies for treatment and management.

In the past 30 years, DKD has become the most common cause of kidney failure and end-stage kidney disease (ESKD), and it is also the main cause of death in diabetics. Early detection helps to overcome treatment inertia and achieve timely medical intervention to maximize the preservation of diabetes. The patient's renal function is essential to avoid ESKD and improve clinical outcomes. These measures are crucial for preventing patients from progressing to ESKD and improving clinical outcomes.

The gold standard for diagnosing DKD is renal biopsy, which offers the highest accuracy. However, due to the invasive nature of renal biopsy, patient acceptance is low, limiting its widespread applicability. It is primarily used when it is difficult to distinguish between DKD and non-diabetic kidney disease, and it is not the preferred diagnostic method for DKD.

Over the past decade, the advent and application of multi-omics technologies, including metabolomics, proteomics, and genomics, has led to a growing recognition of the pivotal roles played by intestinal dysbiosis and intestinal-derived metabolites in the pathogenesis of DKD. The prevailing view in modern medicine is that intestinal flora plays a pivotal role in the digestive process, influencing the synthesis, absorption, and metabolism of nutrients. Additionally, it forms a crucial component of the intestinal barrier, which serves as a vital line of defense against invading pathogens. This concept is also reflected in traditional Chinese medicine, where the spleen is regarded as the primary regulator of physiological functions. In light of these findings, the identification of DKD gut-derived metabolic markers and the restoration of gut flora homeostasis from the perspective of the intestinal flora through the use of multi-omics techniques may represent promising strategies for the prevention and management of DKD.

This study aims to employ microbial metabolomics to gain a deeper understanding of the Traditional Chinese Medicine (TCM) pathogenesis of DKD. It seeks to provide a scientific foundation for this field and to guide TCM theories in the clinical practice of DKD prevention and management.

## 2 Methods

### 2.1 Trial overview, ethical consideration, and patient recruitment

This study is an ongoing, single-center, cross-sectional observational clinical trial. The subjects were selected for observation and subsequent analysis for key biomarkers such as blood glucose, Urine Albumin-to-Creatinine Ratio(UACR), and renal function. Blood, urine, feces, and moss on the tongue samples were collected from the subjects and stored for subsequent analysis. The study protocol was approved by the Ethics Committee of the First Affiliated Hospital of Hunan University of Traditional Chinese Medicine in accordance with the relevant ethical standards. The study is currently being conducted at the First Affiliated Hospital of Hunan University of Traditional Chinese Medicine and involves four groups of participants: type 2 diabetic kidney disease (DKD), type 2 diabetes mellitus (T2DM), chronic kidney disease (CKD), and healthy human. Subjects will be recruited from inpatients or outpatients of the Department of Endocrinology and the Department of Nephrology of the First Affiliated Hospital of Hunan University of Traditional Chinese Medicine. Additionally, healthy human subjects will be recruited from the general public through printed advertisements, invitations, etc. The total number of individuals proposed to be recruited in the four groups is 720.

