### 2.2 Study outcomes

**Primary outcome:** By employing a combination of microbiomic and metabolomic technologies, we conducted a comprehensive analysis of the intestinal flora and serum metabolic profiles associated with DKD. This approach enabled us to identify potential enterogenous disease markers of DKD and to investigate the metabolic profiles that may be linked to disease progression.

**Secondary outcome:** The objective of this study is to analyze the interaction between intestinal flora and intestinal-derived metabolites in the disease process of DKD. Additionally, the aim is to provide new disease diagnostic strategies and progression risk assessment indicators for diabetic nephropathy, which can be applied to early identification, precise diagnosis, and prognosis of the disease.

**Exploratory outcomes :** In accordance with the test results, each group will select four to six remaining fecal samples as the donor source for allogeneic fecal bacteria transplantation. Subsequently, the correlation between intestinal flora and enteric metabolites in diabetic nephropathy will be investigated through the method of human-mouse allogeneic flora transplantation.

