### 2.4 Study procedures

#### 2.4.1 Questionnaire to collect information

(1) General items: name, gender, age, BMI, education level, labor intensity, dietary preferences, etc;

(2) TCM symptoms, tongue and pulse;

(3) Clinical information: disease duration, other complications (e.g., diabetic peripheral neuropathy, diabetic retinopathy, diabetic cardiomyopathy, etc.), concomitant diseases (hypertension, coronary artery disease, hyperlipidemia, cerebrovascular disease, and hyperuricemia, etc.), past medical history, history of smoking, alcohol, family history, and history of drug use.

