#### 2.4.2 Outcome Measures

Indicators of safety: Physical examination (including general condition, blood pressure, heart rate, heart rhythm, body temperature, respiratory rate, etc.) was

performed before taking the samples to assess the basic condition of the subjects.

**Primary Outcome Measures :** Urine Albumin-to-Creatinine Ratio(UACR), Estimated Glomerular Filtration Rate(eGFR),blood urea nitrogen(BUN), serum creatinine(Scr), fasting blood glucose(FBG), Glycosylated Hemoglobin, Type A1C(HbA1c), glucosylated serum protein(GSP) , etc. Test data were obtained from test results conducted within one month of enrollment for the purpose of evaluation.

**Secondary Outcome Measures:** 16S ribosomal DNA(16S rDNA) identification, metagenomic Next Generation Sequencing, Non-targeted and targeted Metabolomics technology detection , etc.

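### Patients may be sampled as inpatients while healthy volunteers are not, and neither care setting nor time since admission is fixed, listed or used in the analysis

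*Combined protocol and SAP*

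**What the plan says.** Section 2.1 gives the two recruitment routes. For the disease groups: "Subjects will be recruited from inpatients or outpatients of the Department of Endocrinology and the Department of Nephrology". For the controls: "healthy human subjects will be recruited from the general public through printed advertisements, invitations, etc". There is no quota, balancing or restriction by care setting.

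On sampling, section 2.1 says only "Blood, urine, feces, and moss on the tongue samples were collected from the subjects and stored for subsequent analysis". The one time window is in section 2.4.2: "Test data were obtained from test results conducted within one month of enrollment for the purpose of evaluation". It governs the clinical laboratory values, not the stool and serum used for sequencing and metabolomics.

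The questionnaire in section 2.4.1 collects "General items: name, gender, age, BMI, education level, labor intensity, dietary preferences, etc", and then disease duration, complications, concomitant diseases and "past medical history, history of smoking, alcohol, family history, and history of drug use". Inpatient or outpatient status, admission date and length of stay are not listed.

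Section 2.5 assigns unadjusted two-group tests to the clinical indicators. For the omics data it names methods, including MaAsLin, a permutation-type multivariate analysis (printed as ERMANOVA) and random forest. It names no covariate, matching, stratification or sensitivity analysis.

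**The concern.** The primary outcome in section 2.2 is a "comprehensive analysis of the intestinal flora and serum metabolic profiles associated with DKD", from which gut-derived disease markers are to be identified. Both stool and serum can change during a hospital stay. A patient sampled several days after admission has eaten ward food, moved less and may have had treatment changed. A volunteer answering an advertisement has not.

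In any patient-versus-healthy contrast, hospital exposure can therefore occur on one side only, and whatever it does to a feature is added to the disease difference. In DKD versus T2DM or DKD versus CKD, the same happens if one group has more inpatients or longer stays before sampling. That is possible, because the groups are drawn from two departments.

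Correcting for multiple testing would not help, because this is bias and not chance. The stool chosen as donor material for the exploratory mouse transplantation comes from the same participants, so a setting effect could carry over there as well.

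**Working it through.** **Step 1: which hospital influences the exclusions already remove.** Section 2.3.3, items (1) to (5), set against the plausible routes:

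- Removed or reduced: infection or other acute disease in the past month (1), a state of stress (2), other unstable chronic disease (3), gastrointestinal disease (4), and systemic antibiotics, immunosuppressants, chemotherapy or chronic proton pump inhibitor treatment in the past three months (5).
- Not addressed: ward diet, inactivity and short-term changes in other treatment. Inpatients remain expressly eligible.

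The exclusions narrow the effect but do not close it.

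**Step 2: inputs for a sense of scale.**

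- Total size, section 2.1: "The total number of individuals proposed to be recruited in the four groups is 720". The split is not stated; 720/4 = 180 per group is an assumption. The plan gives no power, effect size, SD or dropout, so 720 cannot be reproduced. The point does not depend on it.
- Significance level 0.05, section 2.5. Two-sided is assumed, because sidedness is stated only for the normality and variance tests.
- Inpatient shares p₁ and p₂ in the two groups, and the hospital shift d in SD units: not in the documents, so varied.

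**Step 3: formulae, with no true disease effect.**

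- Bias: b = (p₁ − p₂) × d
- Standard error: SE = √{[2 + p₁(1 − p₁)d² + p₂(1 − p₂)d²]/180}
- Chance of a significant result: Φ(b/SE − 1.96) + Φ(−b/SE − 1.96)

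**Step 4: patients against healthy (p₂ = 0).**

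- d = 0.2, p₁ = 0.30: b = 0.06, SE = √(2.0084/180) = 0.1056, b/SE = 0.57. Result: Φ(−1.39) + Φ(−2.53) = 0.082 + 0.006 = 0.088, about 9%.
- d = 0.5, p₁ = 0.60: b = 0.30, SE = √(2.06/180) = 0.1070, b/SE = 2.80. Result: Φ(0.84) = 0.80, and the other tail is negligible.

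| Shift d | 30% inpatients | 50% | 60% | 80% |
|---|---|---|---|---|
| 0.2 SD | 9% | 16% | 21% | 33% |
| 0.3 SD | 14% | 29% | 40% | 62% |
| 0.5 SD | 29% | 65% | 80% | 96% |

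Simulated t-tests (40,000 runs per cell) agree with this table to within about one percentage point.

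**Step 5: one patient group against another, d = 0.5.**

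- Equal shares: b = 0, so 5%.
- 50% against 40%: about 7.5%.
- 50% against 25%: about 21%.
- 70% against 40%: about 28%.

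**Step 6: price of restricting to outpatients.** With 60% inpatients, 180 × 0.4 = 72 outpatients remain per patient group. The standard error in SD units rises from √(2/180) = 0.105 to √(1/72 + 1/180) = 0.139 against 180 healthy subjects, and to √(2/72) = 0.167 between two patient groups. The difference detectable with 80% power (2.80 × SE) rises from 0.30 SD to 0.39 and 0.47 SD.

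**The case against.** The strongest reply has four parts.

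- *The plan already screens out the main hospital influences.* This is partly right. Items (3) to (5) of section 2.3.3 matter as much as items (1) and (2), and the drug-use history in 2.4.1 may capture some treatment changes. They make a small shift more credible than a large one. They do not cover diet, inactivity or short-term changes in other drugs.
- *Care setting is retrievable.* A reader might infer that it is not recorded and could never be adjusted for. The documents do not support that. The general-items list is open-ended, and a hospital holds admission dates for its own inpatients. What can be said is that setting is not listed and that nothing commits the study to using it.
- *The T2DM and CKD groups come from the same hospital.* A general hospital effect would tend to appear in all three disease groups, so a feature specific to DKD is partly protected. A reader might infer that every contrast involving patients is biased, or that affected features will necessarily be named DKD markers. Neither follows: between-patient contrasts are biased only if inpatient share or time in hospital differs, the documents give no shares, and no rule for naming a marker is stated.
- *The percentages are not those of the planned marker analysis.* Correct. Section 2.5 assigns the t-test to clinical indicators and other methods to the omics data. The figures show scale only.

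What remains is the one-sided exposure against healthy controls, with no sampling window and no planned analysis of setting.

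**Conclusion.** The concern holds in a limited form. Following the plan as written, any hospital effect on flora or serum is confounded with disease in the patient-versus-healthy contrasts. It is confounded in DKD versus T2DM or CKD only where inpatient share or time in hospital differs.

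The size cannot be determined from the documents. Under the stated assumptions (180 per group, two-sided 0.05, a simple two-group test, no disease effect), the false-positive rate per affected feature against healthy controls runs from about 9% (0.2 SD, 30% inpatients) to about 80% (0.5 SD, 60% inpatients). If between-group shares and time in hospital are equal, it stays at 5%. This is worth correcting because the affected quantities are the primary outcome and the study is still under way.

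**What to change.** 1. **Data (2.4.1).** Record care setting, admission date and sampling date for every patient. For those already enrolled, take these from hospital records.
2. **Sampling (2.1 or 2.4).** For future inpatients, collect stool and research blood as early as possible after admission. This cannot help participants already sampled.
3. **Patient-versus-patient models (2.5).** Include setting as a term in the MaAsLin and permutation-based models.
4. **Sensitivity analysis (2.5).** Repeat the DKD marker contrasts, including DKD versus healthy, in outpatients only. Restriction is the clearer tool against healthy subjects, because inpatients have no healthy counterpart to be adjusted against. Report markers whose direction or size changes materially as possibly due to setting. Do not make persistence in outpatients a pass-or-fail rule, since a true marker could fail through imprecision alone.

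The cost is three data fields, one sampling instruction, one model term and one further analysis. There are two downsides. The outpatient analysis is smaller and less precise. Setting may also track disease severity, so adjusting or restricting can take away part of a real disease signal. For that reason, adjusted and unadjusted results should be shown side by side.

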### 2.2 Study outcomes

**Primary outcome:** By employing a combination of microbiomic and metabolomic technologies, we conducted a comprehensive analysis of the intestinal flora and serum metabolic profiles associated with DKD. This approach enabled us to identify potential enterogenous disease markers of DKD and to investigate the metabolic profiles that may be linked to disease progression.

**Secondary outcome:** The objective of this study is to analyze the interaction between intestinal flora and intestinal-derived metabolites in the disease process of DKD. Additionally, the aim is to provide new disease diagnostic strategies and progression risk assessment indicators for diabetic nephropathy, which can be applied to early identification, precise diagnosis, and prognosis of the disease.

**Exploratory outcomes :** In accordance with the test results, each group will select four to six remaining fecal samples as the donor source for allogeneic fecal bacteria transplantation. Subsequently, the correlation between intestinal flora and enteric metabolites in diabetic nephropathy will be investigated through the method of human-mouse allogeneic flora transplantation.

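### No prespecified analysis in the human study separates gut production from reduced renal clearance, so a retained serum solute may be labelled enterogenous

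*Combined protocol and SAP*

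**What the plan says.** All references are to the combined protocol and SAP.

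- **Section 2.2, primary outcome.** The material analysed is a "comprehensive analysis of the intestinal flora and serum metabolic profiles associated with DKD". The result claimed is: "This approach enabled us to identify potential enterogenous disease markers of DKD".
- **Section 2.1.** The study is a "single-center, cross-sectional observational clinical trial" with four groups: "type 2 diabetic kidney disease (DKD), type 2 diabetes mellitus (T2DM), chronic kidney disease (CKD), and healthy human". On size it says only: "The total number of individuals proposed to be recruited in the four groups is 720". The split between groups is not given, and no matching on kidney function is described. On samples: "Blood, urine, feces, and moss on the tongue samples were collected from the subjects and stored for subsequent analysis".
- **Section 2.4.2.** Kidney function is measured, among the primary outcome measures: "Estimated Glomerular Filtration Rate(eGFR),blood urea nitrogen(BUN), serum creatinine(Scr". These results may come from any time within one month of enrollment. The secondary measures include "Non-targeted and targeted Metabolomics technology detection", with no sample type stated.
- **Section 2.5.** Clinical indicators get unadjusted two-group tests. Flora and metabolites get a list of methods: Spearman, network, Procrustes, MaAsLin, ERMANOVA and random forest. No covariate is named for any of them, and nothing defines an enterogenous marker.
- **Section 2.2, exploratory outcome.** Four to six leftover stool samples per group, chosen in the light of the test results, go into a human-to-mouse flora transplantation.

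**The concern.** The concentration of a solute in serum depends on how fast it is made and how fast it is cleared. DKD and CKD reduce clearance, so a solute can rise in serum wherever it is made. If the abundance of a taxon also varies with kidney function, taxon and solute share a common correlate and are associated through it, even among DKD patients alone. Analysing the groups separately does not remove this. Nor does adjusting for age, BMI, diet or drugs, because the shared variable is filtration. The cross-sectional design gives no time order to help.

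At stake is the word that distinguishes the primary outcome. A serum metabolite that marks DKD because it is retained may still be a useful marker, but it is not evidence for the gut mechanism that Section 1 sets out. As Section 2.5 stands, the two kinds of marker can look the same.

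**Working it through.** **No plan figure to reproduce.** The only sample-size figure is 720 in total. No power, effect size, SD or allocation is given, so it can be neither reproduced nor refuted, and this point does not rest on it.

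**Inputs**

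- From the documents: alpha 0.05 (Section 2.5; two-sided assumed here) and 720 people in four groups (Section 2.1).
- Assumed: an equal split, 720 / 4 = 180 DKD patients.
- Assumed: the correlation of eGFR with a serum metabolite (*a*) and with a taxon (*b*), and no other link between metabolite and taxon.

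**Induced correlation.** With eGFR as the only link, r = a × b. By Fisher's z, the expected test statistic is atanh(|r|) × √(n − 3), with √177 = 13.30. The probability of significance is approximately Φ(statistic − 1.96).

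| a | b | r | Statistic | Significant at n = 180 |
|---|---|---|---|---|
| -0.6 | 0.3 | -0.18 | 0.182 × 13.30 = 2.42 | Φ(0.46) = 68% |
| -0.5 | 0.2 | -0.10 | 0.100 × 13.30 = 1.33 | Φ(-0.63) ≈ 27% |
| -0.7 | 0.3 | -0.21 | 0.213 × 13.30 = 2.84 | Φ(0.88) = 81% |
| any | 0 | 0 | 0 | 5% (nominal) |

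Section 2.5 names Spearman, so the first three rows were also simulated with rank correlation (4,000 runs). The rates were 64%, 25% and 76%.

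**Conditioning on eGFR.** The numerator of the partial correlation is r − a × b, which in the first row is -0.18 − (-0.6)(0.3) = 0. In the simulation, a rank partial correlation on eGFR brought the false rate to 5–6%.

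**Second check under different assumptions.** A solute with identical production in all groups was simulated in DKD plus T2DM, 180 each (2,000 runs). Within-group eGFR SD was 20, the strength of the taxon's link to eGFR was 0.2, that of the solute's was 0.3 to 0.5, and the eGFR gap between groups was 10 to 30.

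- Spearman between solute and taxon was significant in 19%, 27% and 75% of runs as the assumptions strengthened, and in 4% when the taxon did not track eGFR.
- With eGFR in the model, the rate was 4.8–5.4%.
- An unadjusted DKD–CKD comparison flagged the solute in 4–6% of runs when mean eGFR was equal in the two groups, but in about 95% when it differed by 15 (solute link 0.5).

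**Limit of adjustment.** If measured eGFR correlates 0.9 with true filtration (assumption), the partial-correlation false rate at n = 180 is 6–12% over the three non-null rows of the table. Adjustment removes most of the problem, not all of it. Results dated up to a month from enrollment would add to this error.

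**The case against.** A reader might infer that the study contains nothing bearing on gut origin, and that retained solutes are bound to be called gut-derived. The documents do not support either reading.

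- **The transplantation** in Section 2.2 could in principle test microbial origin independently of the patient's filtration. It is present. But it is exploratory and small, its donors are chosen after the results, its stated aim is a correlation, and the primary label does not depend on it.
- **The CKD group** is a partial control for low filtration. Section 2.1 gives it no such role and requires no comparability of eGFR, and the check above shows that it protects only when eGFR is comparable.
- **The wording is cautious.** The markers are called potential, and MaAsLin can take covariates. Adjustment is unspecified, not ruled out. That supports saying that mislabelling may occur, not that it will.
- **Serum is not the only possible matrix.** The secondary and exploratory outcomes refer to intestinal-derived and enteric metabolites, stool is stored, and Section 2.4.2 gives no matrix. Fecal metabolomics is neither stated nor excluded.
- **The mechanism needs a taxon that tracks eGFR.** The documents do not say that any does. Without that link the false rate is nominal.
- **Conditioning on eGFR can do harm.** Section 1 gives gut metabolites a role in how DKD arises. If some lower eGFR, adjustment can weaken or distort a real link.

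All six stand as limits on the point. None supplies what is missing: an analysis that takes filtration into account, or a criterion for the label.

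**Conclusion.** The point holds in a limited form. The human study has no prespecified analysis that separates gut production from reduced renal clearance, although it collects the eGFR needed for one, so a retained solute may be labelled enterogenous.

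The size is illustrative. At 180 DKD patients the chance that a pure retention effect gives a significant taxon–metabolite correlation runs from about 5% (taxon unrelated to eGFR) through 27% and 68% to 81%, depending on assumed correlations that the documents do not give. The 180 is also an assumption. No figure is offered for all 720 pooled, because the range of eGFR, and with it the correlations, would differ from those within DKD.

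Two further inferences should be resisted. A taxon link that survives adjustment for eGFR does not prove gut production, since shared diet or drugs could leave a residual association. A DKD–CKD difference at equal eGFR shows disease specificity, not origin: a gut-made solute raised equally in both diseases would fail that test, and a metabolite altered by diabetes anywhere in the body could pass it.

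**What to change.** Add to Section 2.5:

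1. For flora–metabolite associations within DKD, run partial Spearman and MaAsLin with log eGFR as a covariate. Report each result with and without it, because eGFR may lie on the causal path.
2. Keep the unadjusted results for selecting markers. Use the label potential enterogenous only for serum markers whose taxon link persists given eGFR, and call the rest serum markers of DKD.
3. State that persistence is necessary for the label but not sufficient evidence of gut origin. Name agreement with stool metabolites, if these are assayed, and the exploratory transplantation as supporting evidence.
4. Report the eGFR-adjusted DKD–CKD contrast as evidence of disease specificity, not of origin.

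The analysis needs only extra model terms on data that Section 2.4.2 already collects, with no new samples or visits. The price is a shorter enterogenous list, and some true gut-derived markers that act through eGFR may lose the label. Showing both sets of results lets readers see which ones.

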## 2.5 Data analysis

SPSS 26.0 will be applied for statistical analysis of clinical indicators. Data that exhibited a normal distribution were expressed as the mean  $\pm$  standard deviation(  $x \pm s$ ), and an independent samples t-test was employed for comparison between two groups. Data that did not conform to a normal distribution were expressed as the median and interquartile spacing [M(IQP)], and a Mann-Whitney rank-sum test (U test) was used for comparison between two groups. In the case of count data, these were expressed as frequencies or percentages. In the event of unordered categorical count data, comparisons between two groups were performed using either the four-cell table or the column table  $c^2$  test. The Pearson  $c^2$  test or Fisher's exact probability method was employed in accordance with the sample size and the size of the theoretical frequency. In the case of ordered categorical count data, comparisons between two groups were performed using the U test. A two-sided test was employed for the normality test and variance chi-square test, with an alpha level of 0.1. This resulted in the rejection of the original hypothesis, indicating that the data are not normally distributed or that there is no significant variance. For other significance tests, an alpha level of 0.05 was used, leading to the rejection of the original hypothesis and the conclusion that the difference is statistically significant.

An integrated correlation analysis will be performed using a variety of analytical techniques, including intestinal flora species diversity analysis, Spearman's correlation analysis, network analysis, Procrustes analysis, MaAsLin analysis, ERMANOVA analysis, random forest analysis of differential intestinal flora with differential metabolites between groups, and efficacy evaluation.

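### Section 2.2 promises new diagnostic strategies for DKD, but section 2.5 plans no analysis that could show whether an omics panel adds to the clinical data already collected

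*Combined protocol and SAP*

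**What the plan says.** Section 2.2 (secondary outcome) states that "the aim is to provide new disease diagnostic strategies and progression risk assessment indicators for diabetic nephropathy", and gives the intended use: "which can be applied to early identification, precise diagnosis, and prognosis of the disease".

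The study also collects routine clinical data. Section 2.4.1 has "General items: name, gender, age, BMI, education level, labor intensity, dietary preferences, etc", and then "Clinical information: disease duration, other complications", followed by concomitant diseases (including hypertension) and drug history. The laboratory list in section 2.4.2 begins "Urine Albumin-to-Creatinine Ratio(UACR), Estimated Glomerular Filtration Rate(eGFR),blood urea nitrogen(BUN), serum creatinine(Scr), fasting blood glucose(FBG" and goes on to HbA1c and glycated serum protein.

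Section 2.5 treats the two sources in separate paragraphs. For the first, "SPSS 26.0 will be applied for statistical analysis of clinical indicators", by t, Mann-Whitney, chi-square or Fisher tests between two groups. For the second, "An integrated correlation analysis will be performed using a variety of analytical techniques", and the list of techniques ends with "random forest analysis of differential intestinal flora with differential metabolites between groups, and efficacy evaluation". The closing term, on efficacy, is not defined. The section names no clinical-only model, no combined model, no accuracy measure, no validation scheme and no covariates.

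**The concern.** A clinician who faces a patient with diabetes already knows the age, BMI, duration of disease, blood pressure history and HbA1c. A test supports a new diagnostic strategy only if it improves on that knowledge. Stand-alone separation between groups does not answer this, even when it is estimated without optimism, because flora and metabolites may simply track clinical variables that also differ between the groups.

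The data needed to answer the question are in hand, but the planned analysis does not bring them together. A claim of a new diagnostic strategy could then rest on separation that the clinical record already provides.

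**Working it through.** **Inputs from the documents.** Four groups and a total of 720 (section 2.1). The split is not stated; an equal split gives 720 / 4 = 180 per group, which is an assumption. The plan gives no effect size, power, AUC or other accuracy figure, so there is no planned figure to reproduce.

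**Assumed inputs.** The AUC of a clinical score, AUC_c, and the within-group correlation r between that score and the omics panel, both shown over a range.

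**Step 1: how well does a redundant panel separate the groups?** Take normal scores with within-group SD 1. The clinical score differs between groups by d = √2 × z(AUC_c), where z is the standard normal quantile. A panel that carries nothing beyond the clinical score differs by r × d, so its own AUC is Φ(r × d / √2) = Φ(r × z(AUC_c)).

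For AUC_c = 0.80, z = 0.842 and d = 1.19. At r = 0.7 the panel AUC is Φ(0.7 × 0.842) = Φ(0.589) = 0.72, with a Hanley-McNeil 95% interval of 0.67 to 0.77 at 180 versus 180. Over the range:

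| Clinical AUC | r = 0 | r = 0.5 | r = 0.7 | r = 0.9 |
|---|---|---|---|---|
| 0.75 | 0.50 | 0.63 | 0.68 | 0.73 |
| 0.80 | 0.50 | 0.66 | 0.72 | 0.78 |
| 0.90 | 0.50 | 0.74 | 0.82 | 0.88 |

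Every panel in the table adds nothing to the clinical score. The size of the problem depends on r, which the documents do not give and the planned analysis would not estimate.

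**Step 2: would a direct comparison work at this size?** Simulation with 180 versus 180, 1,000 runs per scenario, clinical AUC 0.80 or 0.90, r = 0.5 or 0.7. The likelihood-ratio (LR) test is for the panel added to a logistic model with the clinical score, at the 0.05 level.

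| True added effect of panel | Panel alone significant | LR test significant | Mean AUC gain |
|---|---|---|---|
| none | about 100% | 4.6 to 5.3% | 0.001 |
| 0.3 SD | about 100% | about 50 to 70% | 0.004 to 0.009 |
| 0.5 SD | about 100% | about 92 to 98% | 0.009 to 0.021 |

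The panel-alone test cannot tell the first row from the last. The added-value test can, if the added effect is moderate.

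**Step 3: which statistic should carry the test?** A second simulation used two independent clinical variables that differ by 0.6 and 0.4 SD, an independent panel score and 500 runs. A real added effect of 0.3 SD was detected by the LR test in 76% of runs, but a DeLong 95% interval for the AUC difference excluded zero in only 16%. At 0.5 SD the figures were 99% and 66%. The AUC difference is therefore suited to showing the size of the gain, and the LR test to deciding whether there is one.

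**Limit of the working.** The simulations use one ready-made score fitted in-sample. A random forest that selects its features on the same data would add optimism, which is why the fix needs cross-validation.

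**The case against.** The strongest reply is that this is discovery work. The primary outcome speaks of potential markers, section 2.5 calls the omics work a correlation analysis, and incremental value is a later-stage question. This stands in part: if the sponsor claims only candidate markers, the comparison is not essential. But the diagnostic aim sits under the secondary outcome, while section 2.2 keeps the exploratory label for the transplantation work in mice.

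It could also be said that the undefined efficacy evaluation, or MaAsLin, covers the point. Neither does as written. The first names no comparator. The second is listed without covariates, and an adjusted association for a single feature does not measure added diagnostic value.

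A reader might infer more than the documents support:

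- That a redundant panel has no diagnostic value of its own. It does separate the groups; what it lacks is value beyond the clinical data.
- That a flattering accuracy figure is planned. No accuracy measure is named, so such a report is possible, not scheduled. The same holds for predictive values distorted by the group mix, since the plan proposes none.
- That UACR and eGFR define the groups. Section 2.3.1 cites guidelines and does not say which tests assign a patient to which group.
- That any modest omics AUC is redundant. With clinical differences of 0.6 and 0.4 SD, d = √(0.36 + 0.16) = 0.72 and the clinical AUC is Φ(0.72 / √2) = 0.695. A redundant panel then reaches only 0.60, 0.64 or 0.68 at r = 0.5, 0.7 or 0.9. An AUC near 0.70 with nothing new would need almost perfect correlation.

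**Conclusion.** The concern holds as a gap between aim and analysis: the plan promises a diagnostic deliverable and includes no analysis that could show added value over clinical data the study already holds. With a clinical AUC of 0.75 to 0.90 and a correlation of 0.5 to 0.9, a panel that adds nothing would show an AUC of 0.63 to 0.88 by itself. With no correlation it would show 0.50 and the risk disappears, but only the missing comparison would reveal which case applies.

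The clinical AUCs, correlations, added effects and 180 per group are all assumptions. The documents do not show that the panel will prove redundant or that a misleading figure will be reported. The point covers the diagnostic claim only; it does not settle whether a cross-sectional study can support the progression and prognosis claims. The change is worth making because it is cheap and lets the study answer its own question.

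**What to change.** In section 2.5:

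1. Name DKD versus T2DM and DKD versus CKD as the diagnostic contrasts. The second matters because section 1 places the main use of biopsy in telling DKD from non-diabetic kidney disease. Report DKD versus healthy as description only.
2. For each contrast, fit two models in the same cross-validation folds. Model A holds collected clinical variables that do not define the groups: for example age, gender, BMI, hypertension and, where they do not define the contrast, disease duration and HbA1c. State which tests assign patients to groups, and leave out UACR and eGFR if they are among them. Model B is A plus the omics score, with feature selection inside the folds.
3. Test the out-of-fold omics score added to A with a likelihood-ratio test. Report the cross-validated AUC difference, B minus A, with its confidence interval as the size of the gain.
4. Base any claim of a new diagnostic strategy on this added value. Otherwise describe the result as candidate markers.

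The study is ongoing, so this should be fixed before results are seen. It needs no new data. The cost is a modest amount of extra analysis, and the claim may become less favourable.
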